Study design: The design is a parallel-group randomized controlled trial (RCT) in which each participant is to be randomly assigned to three groups after meeting the eligibility criteria. For the randomization procedure, we will use permuted-block randomization. The three groups of subjects will consist of a group to be given daily oral ranitidine (3mg/kg) for 10 days (oral ranitidine group-ORG), the group that will receive probiotic for 10 days (PBG) and the control group that will be given a placebo (vitamin C- 50mg daily) for the same duration.

Twenty participants will be assigned to each group- ORG, PBG, and PG. A proforma will be used to record the bio-data, anthropometry of participants, and findings of their stool analysis and stool microscopy/culture.

Intervention: In the ORG- participants will be given oral ranitidine (3mg/kg/day) once daily for 10 days; in the PBG, they will receive probiotics in appropriate doses for 10 days; while in the PG,

the participants will be given vitamin C (50 mg) daily for the same duration. We will ensure allocation concealment by using sequentially numbered, opaque, sealed envelopes (SNOSE) containing the medications. In a double-blind fashion, each enrolled participant will be given color-coded envelopes containing ranitidine, the probiotic, or vitamin C tablets unknown to both the caregivers and outcome assessors.

Follow-up/outcome measures: Stool frequency and consistency will be recorded on days 5 and 10. Any adverse drug reactions will be noted on these follow-up days. There will also be follow-up documentation of stool frequency and consistency 30 days after the end of interventions. Failure of participants to present for documentation of the study outcomes on any of the days will be the qualification for dropping out.

Safety considerations: Follow-up on adverse drug reactions (especially adverse reactions related to ranitidine) will be extended up to 60 days after the end of the intervention. Clinical monitoring of participants for adverse reactions to probiotics will be ensured. Provision will be made for hospitalization and appropriate intervention

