Data management and statistical analysis: Data entry and analysis will be done using the Statistical Package for Social Sciences (SPSS) version 25 for Windows. Data will be scrutinized for incorrect information and will be cleaned periodically. The Student's t-test will be used to determine any statistically significant differences in the mean daily stool frequencies of the three intervention groups on the follow-up days. ORG and PBG will be used to report the study effect size. Two standardized measures (Cohen's d and estimation of risk difference) will be used. A 95% confidence interval will be assumed while a p -value < 0.05 will be adopted as the level of statistical significance.

For sample size determination, a predetermined table with the desired statistical power of 0.95 and a Cohen's d (effect size) value of 0.8 will be used, approximating a sample size of 42 (To give room for attrition, 40 will be the final sample size). The value of 0.8 will be chosen to correspond to a large effect size in the predetermined table, indicating the likelihood of a stronger effect.

Study expected outcomes: Normalization of stool frequency and consistency will be the expected outcome of the intervention with oral ranitidine. If no adverse reactions are recorded during and after the study, the intervention may become a paradigm shift in the treatment of toddlers' diarrhea. Clinicians may be more inclined to use this novel pharmacologic approach than the conventional non-pharmacologic methods.

Publication policy/target: We aim to disseminate the findings by publishing them in a reputable international journal within a year of completing the study. [name] will take the lead in the publication. All the investigators will be co-authors.

Duration of research: A proposed period of three years will be allocated for the project implementation and publication of findings. The proposed details include monthly enrollment of eligible participants for 6 months, allocation of participants to intervention groups within a month, follow-up of participants and weekly documentation of outcomes for 6 months, and data analysis for 12 months/manuscript drafting for publication for another 12 months.

Anticipated problems: Seamless participants' enrollment may be affected in the government-run tertiary hospital setting chosen as the study site because of clientele attendance and administrative

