3.0 Medications				
3.1 Probiotic sachets				
3.2 Ranitidine tablets (150 mg)-5x10			210,000	

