3.3 Vitamin C orange-flavored tablets (1 tin of 500 tablets)				
Sub-Total			210,000	210,000

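### The envelopes described do not by themselves secure the caregiver blinding that the protocol claims, because the listed products are not alike and no matching is described

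*Protocol*

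**What the plan says.** The protocol title (General information) describes the trial as double-blind. The Intervention paragraph gives the envelope two tasks.

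- **Allocation concealment:** "We will ensure allocation concealment by using sequentially numbered, opaque, sealed envelopes (SNOSE) containing the medications".
- **Blinding:** participants receive "color-coded envelopes containing ranitidine, the probiotic, or vitamin C tablets unknown to both the caregivers and outcome assessors".

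The same paragraph sets the dosing. In the ranitidine arm, "participants will be given oral ranitidine (3mg/kg/day) once daily for 10 days". The control arm receives a fixed 50 mg of vitamin C daily, and the probiotic dose is described only as appropriate.

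The Part 2 budget, under Medications, lists what is to be bought: "3.1 Probiotic sachets", "3.2 Ranitidine tablets (150 mg)-5x10" and "3.3 Vitamin C orange-flavored tablets (1 tin of 500 tablets".

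The Data management and statistical analysis section compares "mean daily stool frequencies of the three intervention groups on the follow-up days". Under Follow-up/outcome measures, "Failure of participants to present for documentation of the study outcomes on any of the days" counts as dropping out, so outcomes are documented when participants attend. The setting is outpatient, at two clinics.

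**The concern.** Allocation concealment and blinding are separate properties. An opaque, sealed, numbered envelope protects the first: nobody can foresee the next assignment. Its work is done once it is opened. Caregiver blinding has to hold afterwards, for each of the 10 days on which the caregiver handles the product. That depends on the products looking and tasting alike, on a common dosage form, or on a double dummy. The available text describes none of these, yet it says that the contents are unknown to caregivers.

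The color code is a further weakness. The protocol does not say what the colors stand for. If they map to product, recognizing one product reveals every envelope of that color to anyone who knows of it.

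At stake is the credibility of the outcome. Stool frequency over a day in a child aged 1 to 3 years cannot be watched at a clinic visit, so the figures probably come from the caregiver. Masking the outcome assessor gives little protection if the assessor writes down the account of a caregiver who knows, or believes they know, the treatment.

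**Working it through.** The plan gives no figure for blinding that could be reproduced. The check sets the claim beside the products, with a little dose arithmetic.

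**1. What the envelope can do.** Before opening, it hides the assignment. After opening, it hides nothing. The Intervention paragraph adds no other device, so during dosing the claim rests on the products being indistinguishable.

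**2. Are the products alike as listed?**

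| Arm | Form bought (budget) | Dose (Intervention) |
|---|---|---|
| Ranitidine | 150 mg tablets | 3 mg/kg once daily |
| Probiotic | sachets | not specified |
| Vitamin C (placebo) | orange-flavored tablets, strength not given | 50 mg, fixed |

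- Ranitidine against probiotic (secondary objective): tablet against sachet, a difference in form.
- Ranitidine against vitamin C (primary objective): both are bought as tablets. The differences that remain are flavor and weight-based against fixed dosing.

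**3. Can ranitidine be given as the tablet listed?**

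- Weight at which one whole tablet is the right dose: 150 mg / 3 mg/kg = 50 kg.
- Body weights are not in the protocol. Assume 8 to 15 kg for ages 1 to 3 years.
- At 8 kg: 3 x 8 = 24 mg, and 24 / 150 = 0.16 of a tablet.
- At 15 kg: 3 x 15 = 45 mg, and 45 / 150 = 0.30 of a tablet.

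The tablet must be divided or crushed for every participant. The text does not say who does this, or in what form the dose reaches the caregiver.

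**4. Does the budget quantity agree?** The notation 5x10 is ambiguous. If it means 50 tablets, and the ranitidine arm has 20 children for 10 days, there are 20 x 10 = 200 doses and 50 / 200 = 0.25 of a tablet per dose. That is 0.25 x 150 = 37.5 mg, which suits a child of 37.5 / 3 = 12.5 kg. This is consistent with part-tablets being intended. It says nothing about how they are presented.

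**5. From unblinding to the outcome.** The protocol does not state who reports stool frequency and consistency. Outpatient toddlers, daily counts and documentation at attendance together make caregiver report probable. This is an inference.

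**6. Size.** Nothing in the protocol says how many caregivers would recognize their product or how far that would shift their reports. No size can be put on the bias.

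**The case against.** Several points can fairly be made in the protocol's defense.

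- **Purchased form is not dispensed form.** Because ranitidine cannot be given as bought, some preparation must come between purchase and dispensing, and it could make the products alike. This stands as a limit: the budget shows what was to be bought, not what caregivers saw. But the text describes no such step, so the blinding claim has no stated basis.
- **The primary contrast is tablet against tablet.** This stands. A reader might infer that all three products differ in form. They do not. The sachet matters for comparisons with the probiotic, and the case on the primary contrast is weaker.
- **Each caregiver sees one product.** In a parallel design there is nothing to compare it with, and a different product is not automatically a recognized one. This stands. A reader might infer that unblinding is likely or certain, but the protocol supports only that it is possible.
- **The envelope wording could mean that all three are tablets.** The budget says sachets for the probiotic, and no conversion is described. Flavor and dosing would still differ.
- **The detail may sit in pages not available here or in a dispensing procedure.** That is possible, and the point is limited to the available text. But the protocol itself makes the claim and names the device, and the method of blinding is a protocol matter rather than one left to the SAP.

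**Conclusion.** The point holds in a limited form. The protocol claims that caregivers are blinded, and the only device it describes cannot secure this once the envelope is open. The listed products differ clearly for the ranitidine-probiotic comparison. For ranitidine against placebo they differ less, in flavor and in a divided, weight-based dose against a fixed one. The tablet fractions of 0.16 to 0.30 rest on assumed weights of 8 to 15 kg. The need to divide the tablet does not depend on that range, since a whole tablet suits only a 50 kg child.

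The consequence for the results depends on caregivers supplying the stool data, which is probable but not stated. On that condition, both comparisons are open to reporting bias of unknown size and direction.

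Two stronger conclusions might be drawn, and the protocol supports neither. One is that the bias would favor ranitidine: a caregiver could expect benefit from a probiotic or a vitamin as well. The other is that the false-positive rate would rise by a particular amount: any such figure would need an assumed reporting shift that nothing in the protocol anchors. The color-code weakness is also conditional, because the meaning of the colors is not given.

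**What to change.** 1. **Label each envelope with its unique sequential number only, and drop color codes that could map to product.** This costs nothing, since the envelopes are already to be numbered, and it removes a code that could reveal a whole arm.
2. **Where feasible, dispense all three products in a like form,** for example as powder in similar sachets, with ranitidine weighed to 3 mg/kg by someone who has no contact with caregivers and no role in outcome assessment. State this in the Intervention paragraph. It means preparing 40 x 10 = 400 doses, or 3 x 20 x 10 = 600, depending on whether the stated total of 40 or the stated 20 per group holds. That is a real cost in a self-funded trial, so it is optional.
3. **If step 2 is not done, do not claim caregiver blinding.** Remove double-blind from the title and the Intervention paragraph, state that only outcome assessors are masked, say who reports stool frequency and consistency, and interpret caregiver-reported outcomes accordingly. This is a change of wording only.

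None of these steps needs extra participants or visits.

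### Harms are collected as adverse drug reactions, so events judged unrelated to a product may go unrecorded and drop out of any comparison between arms

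*Protocol*

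**What the plan says.** Three sentences in the Protocol's Methodology state what harm is collected.

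- Follow-up/outcome measures, for days 5 and 10: "Any adverse drug reactions will be noted on these follow-up days".
- Safety considerations, for the longer term: "Follow-up on adverse drug reactions (especially adverse reactions related to ranitidine) will be extended up to 60 days after the end of the intervention".
- Safety considerations, for the probiotic: "Clinical monitoring of participants for adverse reactions to probiotics will be ensured".

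For the later outcome contact, Follow-up/outcome measures says "There will also be follow-up documentation of stool frequency and consistency 30 days after the end of interventions". Study expected outcomes then says "If no adverse reactions are recorded during and after the study, the intervention may become a paradigm shift in the treatment of toddlers' diarrhea".

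The Safety considerations paragraph breaks off in the available text, so further safety wording may exist. In what is available, the term adverse event does not appear. Nor is there a definition of a reaction, or a statement that events are recorded whatever their presumed cause.

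**The concern.** Calling something a drug reaction already contains a judgement about cause. If that judgement comes before recording, a fever, rash or admission that seems coincidental need not be entered. In a single child aged 1 to 3 years, an illness caused by the product and one that merely coincides with it can look the same. Randomisation separates them by comparing all events between arms, but only if the events are in the data. No later analysis plan can restore events that were not collected.

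Two features of this protocol add weight. The background section expects side effects at this age to be negligible, which could tilt attribution towards unrelated. And the expected-outcomes text counts an empty record in ranitidine's favour, so the way harms are collected affects the conclusion that the authors hope to draw.

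**Working it through.** The plan states no figure on this point, so there is none to reproduce. The check is a reading of the harm statements, then two illustrations.

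**1. The statements side by side**

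| Statement | Term used | Arms covered | Period |
|---|---|---|---|
| Days 5 and 10 | adverse drug reactions | all | treatment |
| Extended follow-up | adverse drug reactions, ranitidine emphasised | all | to 60 days after treatment |
| Probiotic monitoring | adverse reactions to the probiotic | probiotic | not stated |

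All three use an attributed term. Two tie the reaction to a named product, which supports the causal reading. Together they span the whole safety period, to about day 70 (10 days of treatment + 60).

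**2. What under-recording could do (assumed values)**

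The protocol gives neither event rates nor the share of events that would be judged product-related, so both are assumed. Let *p* be the true proportion of children with an event, *f* the fraction of those events recorded, and *n* the arm size. Children are taken as independent.

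Chance that nothing is recorded in the arm = (1 − *f p*)^*n*. The arm size is 20, from "Twenty participants will be assigned to each group- ORG, PBG, and PG".

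| True rate *p* | *f* = 1 | *f* = 0.5 | *f* = 0.25 |
|---|---|---|---|
| 10% | 0.90^20 = 12% | 0.95^20 = 36% | 0.975^20 = 60% |
| 30% | 0.70^20 = 0.1% | 0.85^20 = 3.9% | 0.925^20 = 21% |

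The protocol also gives 40 as the total, which is 40/3 = 13.3 per arm. With *n* = 13 and *p* = 10%, the chances are 0.90^13 = 25%, 0.95^13 = 51% and 0.975^13 = 72%.

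If *f* is the same in both arms, the recorded risk difference is *f*(*p*₁ − *p*₂). With assumed true rates of 30% and 10%, the true difference of 20 points shrinks to 0.5 × 20 = 10 points or 0.25 × 20 = 5 points.

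**3. What complete recording could deliver**

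These are 95% intervals for a risk difference by Newcombe's method, built from Wilson limits. With no events in an arm, the Wilson upper limit is z²/(n + z²), with z² = 3.84.

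- 0/20 v 0/20: 3.84/23.84 = 0.161, so 0 (−16.1 to +16.1 points).
- 0/13 v 0/13: 3.84/16.84 = 0.228, so 0 (−22.8 to +22.8 points).
- 3/20 v 0/20: the Wilson limits for 3/20 are 0.052 and 0.360. Lower limit: 0.15 − √[(0.15 − 0.052)² + 0.161²] = −0.038. Upper limit: 0.15 + (0.360 − 0.15) = 0.360. The difference is 15 points (−3.8 to +36.0). Two-sided Fisher p = 2 × C(20,3)/C(40,3) = 2 × 1140/9880 = 0.23.

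The event counts are examples. These figures show the precision available after the fix, not the size of the defect.

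**The case against.** The strongest reply is that the defect is inferred from terminology. In a short protocol written by investigators, adverse drug reaction may loosely mean any untoward event on treatment. Nothing available tells staff to leave out events they think unrelated, and the truncated safety paragraph may have held a definition. This stands as a limit: the wording permits the loss but does not prescribe it. If the authors do mean all events, the fix simply says so.

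The second reply is blinding. Allocation is "unknown to both the caregivers and outcome assessors", so they cannot filter events by the product a child actually received. As far as the blinding holds, under-recording should be largely non-differential. That protects against bias in favour of one arm. It does not recover lost events or prevent the shrinkage shown above.

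Third, arms of 13 to 20 children give a wide interval however well harms are collected. That is true and limits the gain. It is also a reason not to lose events and not to read an empty record as reassurance.

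A reader might infer more than the text supports:

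- *That harms cannot be compared between arms at all.* This applies only to unrecorded events. Recorded reactions can be compared.
- *That the vitamin C arm is unmonitored.* The day 5 and 10 sentence and the 60-day sentence are both general. In the latter, ranitidine is emphasised, but the follow-up is not confined to it.
- *That harm collection lapses at the contact 30 days after treatment.* Only stool outcomes are named for that contact, but the 60-day follow-up spans it.
- *That an empty record is a decision rule.* The sentence in Study expected outcomes expresses a hope.

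**Conclusion.** The point holds as a weakness in the collection wording, worth correcting before enrolment. In the available text, all three harm-collection statements use causally attributed terms over the whole safety period. Events judged unrelated may therefore go unrecorded and be absent from any between-arm comparison, and the favourable reading of no recorded reactions becomes easier to reach.

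The number of events at risk cannot be computed from the protocol; the 12%, 36% and 60% above rest on assumed rates and recording fractions. The conclusion assumes that reaction carries its ordinary causal meaning and that the missing part of the safety paragraph does not redefine it. Confidence is medium for those reasons. The documents do not support a claim that events are deliberately excluded or that one arm is favoured.

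**What to change.** In Follow-up/outcome measures and Safety considerations, replace adverse drug reactions with: *all adverse events, including hospitalisations, regardless of suspected cause*. Record them in the same way in all three arms at the contacts already planned: days 5 and 10, 30 days after treatment, and the existing follow-up to 60 days. Make causality a separate field, judged blind to allocation.

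In Study expected outcomes, tie the safety statement to event counts by randomised arm, with confidence intervals, and not to the absence of recorded reactions.

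The cost is a wording change and a few lines for adverse events on the record form; the proforma, as described, names no harm item. No follow-up beyond that already planned is required, though the protocol does not say how the 60-day follow-up is carried out, and that should be settled at the same time. The downside is that more minor, unrelated illnesses will be recorded. The comparison will also stay imprecise, at about ±16 points with no events in two arms of 20 and ±23 points in two arms of 13.

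### One missed outcome day makes a child a dropout: the protocol confuses a missed visit with withdrawal and does not say that the child's other data or later follow-up are kept

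*Protocol*

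**What the plan says.** Under Follow-up/outcome measures, the protocol sets two on-treatment assessments ("Stool frequency and consistency will be recorded on days 5 and 10") and one later assessment ("There will also be follow-up documentation of stool frequency and consistency 30 days after the end of interventions"). The same paragraph then defines attrition: "Failure of participants to present for documentation of the study outcomes on any of the days will be the qualification for dropping out".

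Under Data management and statistical analysis, the groups are to be compared by t-test at each of the scheduled assessments: "The Student's t-test will be used to determine any statistically significant differences in the mean daily stool frequencies of the three intervention groups on the" (the sentence ends by naming those assessments). The section names no analysis set and no treatment of missing outcomes. Attrition appears only in the sample size text: "approximating a sample size of 42 (To give room for attrition, 40 will be the final sample size").

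Under Safety considerations, adverse-reaction follow-up runs to 60 days post-treatment. The text makes no exception for dropouts.

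**The concern.** Missing one visit and leaving a trial are different events. The first costs one observation; the second ends a child's participation. The protocol gives both the same name, and it applies that name to a child who may have attended the other two assessments.

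The consequence depends on what being a dropout means, which the protocol does not say. In ordinary use it means leaving the study. On that reading, a child seen on days 5 and 10 could be lost from the end-of-treatment comparison because of an absence a month later, and a child absent on day 5 might not be assessed again.

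Attendance could well be related to outcome. The protocol itself calls the disorder benign and describes caregivers treating it themselves. A recovered child has little reason to return a month after treatment, and a child who has not improved may be taken elsewhere. Restricting the comparison to full attenders would then be a selection made after randomisation, and the groups would no longer be protected by it.

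The collection side cannot wait for a statistical analysis plan. Such a plan can define who is analysed, but it cannot recover outcomes that were never recorded because a child had been classed as a dropout.

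**Working it through.** **Inputs from the protocol.**
- Three outcome days, as named in the paragraph that contains the rule. The Duration of research text also mentions weekly outcome documentation, but I have not counted that.
- Group size: "Twenty participants will be assigned to each group- ORG, PBG, and PG".
- Design values: "desired statistical power of 0.95 and a Cohen's d (effect size) value of 0.8 will be used".
- Significance level: "p -value < 0.05 will be adopted as the level of statistical significance". Sidedness is not stated; I use two-sided.

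**Assumed input.** The chance m of missing each visit is not in the protocol. I use 5% to 20%, with visits independent.

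**Step 1: the plan's own figure.** The normal formula for two means is n per group = 2(z₀.₉₇₅ + z₀.₉₅)²/d² = 2(1.960 + 1.645)²/0.64 = 40.6, so 41. The exact t calculation gives 41.6, so 42. The protocol's 42 is therefore reproduced, but as a number per group. As a total (21 per group), two-sided power is about 0.72. Moving from 42 down to 40 adds no allowance for attrition.

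**Step 2: children classed as dropouts.** The share seen on all three days is (1 − m)³. At m = 0.10 this is 0.9³ = 0.729, so 27% are dropouts, although only 10% lack data on any given day.

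**Step 3: cost of excluding them.** This uses 20 per group, d = 0.8 and a two-sided t-test at 0.05. Full attendance gives power 0.69.

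| m | Dropouts under the rule | Left if dropouts excluded, 20(1 − m)³ | Power | Left if all seen that day are used, 20(1 − m) | Power |
|---|---|---|---|---|---|
| 5% | 14% | 17.1 | 0.62 | 19 | 0.67 |
| 10% | 27% | 14.6 | 0.55 | 18 | 0.65 |
| 15% | 39% | 12.3 | 0.48 | 17 | 0.62 |
| 20% | 49% | 10.2 | 0.40 | 16 | 0.59 |

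The fair comparison is between the two power columns, because missed visits cost data under any rule. At m = 10%, power falls by 0.693 − 0.645 = 0.048 from the missed visits themselves. Excluding dropouts costs a further 0.645 − 0.549 = 0.096.

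**Step 4: sensitivity to group size at m = 10%.** The protocol is not consistent on this: 40 children in total across three groups is 13.3 each.
- 13.3 per group: 9.7 left (power 0.39) if dropouts are excluded, against 12.0 (0.47).
- 40 per group, if the 40 is read that way: 29.2 left (0.85), against 36 (0.92).

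**Step 5: sensitivity to independence at m = 10%, 20 per group.**
- If the same children miss every visit, dropouts are 10%, 18 per group remain, and the rule costs nothing extra.
- If no child misses twice, dropouts are 3 × 10% = 30%, and 20 × 0.70 = 14 per group remain (power 0.53).

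**Step 6: bias.** The documents give no attendance figures by outcome or by group, so neither the size nor the sign of any bias can be calculated.

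**The case against.** The strongest reply is that the sentence only defines a term. A reader might infer that recorded data will be thrown away and that the analysis is confined to full attenders, but the protocol says neither. Its t-tests on the follow-up days are compatible with using whoever was seen on each day. Analysis sets and missing-data methods are commonly left to a statistical analysis plan, which is not at hand. This stands: the exclusion is a condition here, not a fact.

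A reader might also infer that the rule takes children out of safety follow-up. The documents do not support that. The 60-day adverse-reaction follow-up is stated without exception, and nothing says it ends for a dropout.

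Nor can a worked bias example be held against the rule merely because non-responders in one group stay away. A child who misses a day has no outcome for that day whatever the child is called, so the same distortion arises in any analysis of observed cases. The rule adds bias only where it removes a child from a day that was attended. The direction is also open, since both recovered and unimproved children may have reason not to come.

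Finally, the missed-visit rates are assumed, and clustering of absences in the same families would shrink the loss.

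What the reply does not remove is the rule itself. It is stated, not left open; it merges two different events; and nothing in the protocol keeps these children in outcome follow-up or in the analysis.

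**Conclusion.** The point holds in conditional form. The protocol defines dropping out by a single missed outcome day and does not say that recorded data are kept or that outcome assessment continues. If dropouts are excluded, the comparison is limited to full attenders, with avoidable loss of data and exposure to attrition bias of unknown size and direction.

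With 20 per group, d = 0.8, two-sided 0.05 and an assumed 10% of visits missed independently, the avoidable loss is about 3.4 children per group (18 − 14.6) and about 0.10 in power. Over assumed rates of 5% to 20% the avoidable power loss runs from about 0.05 to 0.19 (0.670 − 0.623 and 0.591 − 0.404). It is zero if absences fall entirely on the same children. The sample size has no reserve to absorb it.

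**What to change.** Replace the dropout sentence in the protocol with wording to this effect:

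- A missed assessment is a missing observation for that day only. Withdrawal is a separate event, recorded with its date and reason.
- Outcome and safety follow-up continue after a missed visit. Asking the caregiver for the stool count by telephone is one practical way to limit the gaps.
- Every randomised child is analysed in the assigned group, using all recorded days. A mixed model over days 5, 10 and 40 (30 days after the 10-day course) is one option among several.
- A sensitivity analysis addresses missing outcomes, for example by counting non-attenders as not normalised. Because recovered children may also stay away, this is a check on the result and not the main analysis.

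The cost is a change of protocol wording, slightly more analysis work and, if telephone contact is adopted, a few calls.
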